## Trademark Information

Trademarks of the GlaxoSmithKline group of companies	Trademarks not owned by the GlaxoSmithKline group of companies
NONE	CloepK Enter-Test SAS WinNonlin

**10.14. Appendix 8: Protocol Amendment History**

The Protocol Amendment Summary of Changes Table for the current amendment is located directly before the Table of Contents (TOC).

1. INTRODUCTION

The purpose of this reporting and analysis plan (RAP) is to describe the analyses to be included in the Clinical Study Report for Protocol 208436:

Protocol Revision Chronology:		
Original Document Number: 2018N385133_00	Dated: 09-JAN-2019	Version: Original
Original Document Number: 2018N385133_01	Dated: 19-MAR-2019	Version: Amendment 01

2. SUMMARY OF KEY PROTOCOL INFORMATION

2.1. Changes to the Protocol Defined Statistical Analysis Plan

There were no major changes or deviations to the originally planned statistical analysis specified in the Original Protocol 208436 (Dated: 09-Jan-2019) and the Amendment 01 (Dated: 19-Mar-2019).

A minor change is made to the first secondary objective where trough plasma concentration (C_{tau}) is removed from the SAD part and added to the MAD part after confirmation from the Study Pharmacokineticist.

2.2. Study Objective(s) and Endpoint(s)

Objectives	Endpoints
Primary Objectives	Primary Endpoints

 To evaluate the safety and tolerability of single and repeat doses of GSK3186899 in healthy participants 	
 Adverse event reporting, clinical laboratory safety data, physical examinations, vital signs, 12 lead ECGs, 24 hr telemetry
Secondary Objectives	Secondary Endpoints

 To evaluate the systemic pharmacokinetic (PK) profile of single (fasted and fed) and repeat doses of GSK3186899 in healthy participants 	
 Plasma concentrations of GSK3186899 plus derived parameters, as data allow. For SAD part: Derived PK parameters for GSK3186899 following single dose (fasted and fed) including area under the plasma drug concentration versus time curve ($AUC(0-t)$, $AUC(0-\infty)$), maximum observed plasma drug concentration (C_{max}), time to maximum observed plasma drug concentration (T_{max}), and apparent terminal half-life ($T_{1/2}$) as data allow. Predicted accumulation Ratio (AR_{pred})[#] will be calculated. For MAD part: $AUC(0-t)$, $AUC(0-\infty)$, $AUC(0-\tau)$, C_{max}, trough plasma concentration (C_{tau}), T_{max} and $T_{1/2}$.

 To examine dose proportionality following single and multiple doses of GSK3186899 	
 Dose-proportionality assessment using derived PK parameters, as data allow: For SAD part: $AUC(0-\infty)$, C_{max}

Objectives	Endpoints
	For MAD part: AUC(0-tau), C _{max} , C _{tau}

 To assess accumulation and time-invariance ratios of GSK3186899 after multiple doses 	
 Accumulation ratios assessment*, where data allow: RAUC(0-tau), RC_{max}, RC_{tau}. Time-invariance ratio calculation as AUC(0-12)[†] on day 10 to AUC(0-∞) on day 1.
Exploratory Objectives	Exploratory Endpoints

 To collect residual plasma following GSK3186899 analysis, and urine samples, for analysis of metabolites of GSK3186899 	
 Metabolites of GSK3186899 in plasma and urine. These analyses will be detailed in a separate analysis plan.

 To collect bile sample for analysis of metabolites of GSK3186899 (Part A fed regimen only) 	
 Metabolites of GSK3186899 in bile. These analyses will be detailed in a separate analysis plan.

* Accumulation ratios calculated as the ratio of last dose to first dose PK parameters: RAUC(0-tau) = AUC(0-tau) on last dose to AUC(0-tau) on first dose, RCmax = Cmax on last dose to Cmax on first dose, RCtau = Ctau on last dose to Ctau on first dose. # ARpred = 1/(1-e^(k*tau)) where k is elimination rate constant following the single dose and tau is the dosing interval for the intended repeat dosing.

† It is AUC(0-12) if dosing is BID, or, AUC(0-8) if dosing is TID.

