
 
• To collect residual plasma following GSK3186899 analysis, and urine samples, for analysis of metabolites of GSK3186899
 
• To collect bile samples for analysis of metabolites of GSK3186899 (Part A Cohort 3 only)
 
	
 
• Metabolites of GSK3186899 in plasma and urine. These analyses will be run and reported separately from this protocol.
 
• Metabolites of GSK3186899 in bile. These analyses will be run and reported separately from this protocol.
 

\* Accumulation ratios calculated as the ratio of last dose to first dose PK parameters:  $RAUC_{(0-\tau)} = AUC_{(0-\tau)} \text{ on last dose to } AUC_{(0-\tau)} \text{ on first dose}$ ,  $RC_{max} = C_{max} \text{ on last dose to } C_{max} \text{ on first dose}$ ,  $RC_{\tau} = C_{\tau} \text{ on last dose to } C_{\tau} \text{ on first dose}$ . #  $AR_{pred} = 1/(1-e^{(k*\tau)})$  where  $k$  is elimination rate constant following the single dose and  $\tau$  is the dosing interval for the intended repeat dosing.

**Overall Design:** This study will be a randomized, double-blind (sponsor unblinded), placebo-controlled, 2-part study of the oral administration of GSK3186899 in healthy participants. As this will be the first time GSK3186899 is administered to humans, the study design may change based on emerging data as the study progresses.

This study is planned to include approximately 54 participants and will consist of 2 parts:

- Part A will include a single-ascending, sequential crossover design in up to 3 cohorts of participants (Cohorts 1, 2 and 3). Part A Cohorts 1-2 will comprise of a 4-way crossover which includes 4 dosing regimens under fasted conditions. Part A Cohort 3 will comprise of a 2-way crossover which includes 1 dosing regimen under fasted conditions and 1 regimen under fed conditions. The fed conditions regimen will investigate the effect on safety, tolerability and PK of a single dose of GSK3186899 following food administration.

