## 5.4. Scientific Rationale for Study Design

This study will be the first administration of GSK3186899 in human participants. The primary purpose of the current study is to characterise the safety and tolerability of GSK3186899 in healthy participants within a controlled PK range. The study will additionally seek to understand the secondary and exploratory endpoints. Specific scientific considerations which contribute to the study design include:

- In Part A, this study employs a randomized sequential crossover design to allow for dose comparison between and within participants at different dose levels. In addition, this design minimises participant numbers across the SAD part of the

study and allows for a shorter washout period between doses of an individual Cohort as the estimated half-life of GSK3186899 is ~1.3 hours.

- In Part A, the study employs a repeat of Dose Level 4 in Cohorts 1 and 2, the rationale for this is to understand potential variability of drug exposure between different cohorts of participants as the projected bioavailability for GSK3186899 varies between 4-100%.

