**Table 3 Predicted human blood PK parameters for GSK3186899 that were employed for simulation of human PK profile**

Parameter	Predicted Value	%CV #
Clearance (mL/hr/kg)	438	50
Vdss (mL/kg)	800	30
KA (hr-1)	0.7	10
F (%)	50	NA

[figure not shown]
# assumed variability for human PK simulation; NA not applicable

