8.1.1.2. Derived Pharmacokinetic Parameters

Pharmacokinetic parameters will be calculated by standard non-compartmental analysis according to current working practices and using the currently supported version of WinNonlin version 8.0. All calculations of non-compartmental parameters will be based on actual sampling times.

For dose escalation meeting and interim analysis planned sampling times may be used if actual timepoints are not available.

Pharmacokinetic parameters listed will be determined from the plasma concentration-time data, provided there is enough evaluable data available for the calculations. If the concentration data is available partially, then based on scientific judgement the data will be assessed for inclusion or exclusion from the analysis.

Parameter	Parameter Description
Plasma PK Parameters:	
Cmax	Maximum observed concentration, determined directly from the concentration-time data.
RCmax	Ratio of Cmax on last dose to Cmax on first dose, i.e., $RCmax = \frac{Cmax \text{ on the last dose}}{Cmax \text{ on the first dose}}$
Ctau	Trough concentration determined directly from the concentration data (only for Part B of the study). It will be the concentrations at 12h or 8h after first dose (if BID or TID administration, respectively) and always concentration at pre-dose on the last dose.
RCtau	Ratio of Ctau on last dose to Ctau on first dose, i.e., $RCtau = \frac{Ctau \text{ on the last dose}}{Ctau \text{ on the first dose}}$
tmax	Time to reach Cmax, determined directly from the concentration-time data.
tlag*	Lag time before first observation of drug concentrations (after single dose only)

Parameter	Parameter Description
Tlast*	Time of last quantifiable concentration
t _{1/2}	Apparent terminal half-life will be calculated as: $t_{1/2} = \frac{\ln 2}{\lambda_z}$ (NOTE: λ _z is the terminal phase rate constant).
AUC(0-24h)	Area under the concentration-time curve from time zero to 24 hours post-dose (after single dose only).
AUC(0-t)	Area under the concentration-time curve from time zero to the time of the last quantifiable concentration (C(t)) will be calculated using the linear trapezoidal rule for each incremental trapezoid and the log _e trapezoidal rule for each decremental trapezoid.
AUC(0-tau)	Area under the concentration-time curve from time zero to the time of the trough concentration (C(tau)) will be calculated for Part 2 of the study only (repeat dose) using the linear trapezoidal rule for each incremental trapezoid.

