RAUC(0-tau)	AUC(0-tau) on last dose to AUC(0-tau) on first dose $RAUC(0 - \tau) = \frac{AUC(0 - \tau) \text{ on the last dose}}{AUC(0 - \tau) \text{ on the first dose}}$
AUC(0-∞)	Area under the concentration-time curve extrapolated to infinity will be calculated (after single dose only) as: $AUC(0 - \infty) = AUC(0 - t) + \frac{C(t)}{\lambda_z}$ (NOTE: λ _z is the terminal phase rate constant. % of the extrapolated area should not exceed 20%. Any value of AUC(0-∞) derived with more than 20% extrapolation should be flagged and excluded from summary statistics if >30%).
AR _{pred}	AR _{pred} is calculated as : $ARpred = \frac{1}{1 - e^{k * \tau}}$ where k is elimination rate constant following the single dose and tau is the dosing interval for the intended repeat dosing.
R ² adjusted*	The goodness of fit statistic for the terminal elimination phase, adjusted for the number of points used in the estimation of λ _z .
λ _z	λ _z is the terminal phase rate constant. A minimum number of three data points in the terminal phase will be used starting at any post-Cmax data point. The adjusted correlation coefficient (R ² adjusted) in general should be greater than 0.90. Any value < 0.90 but ≥ 0.8 will be flagged but may be used at the PK Scientist's best knowledge and judgment, any value <0.8 should be considered for exclusion from the statistical analysis. All the derived parameters that include λ _z in their calculation (i.e. t _{1/2} , AUC(0-∞)) will need to be flagged or excluded from statistical analysis accordingly. The interval used to determine λ _z should be equal or greater than 1.5-fold the estimated half-life or otherwise flagged and used at the PK Scientist's best knowledge and judgment.
λ _z upper limit*	The upper limit on time for values to be included in the calculation of λ _z .

Parameter	Parameter Description
λz lower limit*	The lower limit on time for values to be included in the calculation of λz
λz number of points*	The number of time points used in computing λz .
% AUC _{ex} *	Percent of AUC _∞ that is extrapolated beyond last quantified concentration
CL/F*	The apparent clearance will be calculated only for Part 1 of the study (single dose) as Dose/ AUC(0-∞)
CL _{ss} *	The apparent clearance at steady state will be calculated only for day 10 Part 2 of the study (repeat dose) as Dose/ AUC(0-tau)
Urine PK Parameters:	
$A_e(t_{1-tz})^*$	Amount excreted in the urine at each interval collection (24 h)

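### The predicted accumulation ratio has the wrong sign in its exponent in both documents, so it is negative for every half-life and dosing interval

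*SAP*

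**What the plan says.** ARpred is listed with the secondary PK endpoints of the single-dose part in the protocol synopsis, protocol section 4 and SAP section 2.2. The formula is printed four times, always with a positive exponent:

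- SAP 2.2, footnote: "ARpred = 1/(1-e^(k*tau)) where k is elimination rate constant following the single dose and tau is the dosing interval".
- SAP 8.1.1.2, derivation table, as a typeset equation that begins "ARpred = \frac{1}{1 - e^{k * \tau", with the legend "where k is elimination rate constant following the single dose and tau is the dosing interval for the intended repeat dosing".
- Protocol synopsis, footnote to the objectives table, beginning "AR_{pred} = 1/(1-e^{(k*\tau".
- Protocol section 4, the same footnote.

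The rate constant is positive elsewhere in the same derivation table. "Apparent terminal half-life will be calculated as" ln 2 divided by lambda_z, and AUC(0-∞) is AUC(0-t) plus C(t)/lambda_z. Neither document defines k as a negative slope, and neither prints the formula with a negative exponent.

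In SAP 8.1.1.2 an asterisk marks the parameters that are only listed. ARpred has no asterisk. SAP 8.1.2 says that all derived PK parameters are summarised. SAP 8.1.5 asks for the geometric mean and the standard deviation of the log-transformed values for all but Tmax and half-life, and SAP 10.5.3 names those same two as the only parameters left untransformed.

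**The concern.** An accumulation ratio compares exposure at steady state with exposure after the first dose. It cannot be negative. Under the usual one-exponential prediction it cannot fall below 1, because some drug from earlier doses always remains. The SAP reads accumulation ratios in the same way: the mock shell for Table 4.10 treats 1 as no accumulation and values above 1 as accumulation. The printed ARpred formula can never return 1 or more when k and tau are positive.

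At stake is the validity of one pre-specified secondary endpoint. Followed literally, the untransformed Part A parameter summary (Table 4.3) would show impossible values, and the log-transformed summary (Table 4.5) could not be produced for ARpred, because negative numbers have no logarithm. The quantity is the single-dose forecast for the intended repeat-dose interval, and that forecast would be lost.

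**Working it through.** **Inputs**

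- Half-life: "the estimated half-life of GSK3186899 is ~1.3 hours" (protocol 5.4). Then k = ln 2 / 1.3 = 0.533 per h.
- Cross-check of k from protocol Table 3: clearance 438 mL/h/kg and volume 800 mL/kg give k = 438/800 = 0.5475 per h, a half-life of 1.27 h. The constant is positive.
- tau: 12 h for twice-daily dosing (protocol 5.1). For three-times-daily dosing, protocol Appendix 5 has 7 h between doses, while SAP 2.2 uses an 8 h AUC. Once-daily dosing is 24 h.
- Half-lives of 3 h and 5 h are assumptions, used to show the range. The documents do not predict them.

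Neither document states a numerical ARpred, so there is no printed figure to reproduce.

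**Sign.** With k > 0 and tau > 0, e^(k·tau) > 1. The denominator 1 − e^(k·tau) is therefore below zero, and so is the ratio.

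**Relation to the correct ratio.** Write x = k·tau. The correct form is 1/(1 − e^(−x)) = e^x/(e^x − 1) = −e^x/(1 − e^x). Adding the printed form gives (1 − e^x)/(1 − e^x) = 1. So the printed value is always 1 minus the correct value.

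**One case in full.** Half-life 1.3 h, tau 12 h: x = 0.5332 × 12 = 6.398 and e^x ≈ 600.8. Printed: 1/(1 − 600.8) = −0.0017. Correct: 1/(1 − 1/600.8) = 1.0017.

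| Half-life (h) | tau (h) | k·tau | As printed | With e^(−k·tau) |
|---|---|---|---|---|
| 1.3 | 7 | 3.732 | −0.0245 | 1.0245 |
| 1.3 | 8 | 4.266 | −0.0142 | 1.0142 |
| 1.3 | 12 | 6.398 | −0.0017 | 1.0017 |
| 1.3 | 24 | 12.797 | −0.000003 | 1.000003 |
| 3 (assumed) | 8 | 1.848 | −0.187 | 1.187 |
| 5 (assumed) | 12 | 1.664 | −0.234 | 1.234 |

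Over a wider grid (eight half-lives from 0.5 to 100 h, at tau 7, 8, 12 and 24 h) the printed formula was negative at all 32 points, and the two forms summed to 1 at each.

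**Consistency check.** Protocol 5.5.2 reports that its simulations show no evident accumulation, so a ratio close to 1 is expected. The corrected formula gives 1.0017 for twice-daily dosing at 1.3 h. The printed formula gives a value close to 0.

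**The case against.** The algebra is not open to dispute, but the weight given to the error is. ARpred enters no model, test or sample-size calculation. The PK stopping criteria (protocol 8.1.1) rest on AUC and Cmax, and the choice of repeat doses (protocol 5.5.5) rests on single-dose exposures and margins to the NOAEL. Observed accumulation is analysed from Day 10 and Day 1 data in Part B (SAP 8.4), in different participants, and neither document plans a formal comparison of ARpred with those ratios. Protocol 10.5.2 does not include ARpred in its list of parameters to be determined. SAP 10.5.3 gives all PK derivations to the pharmacokineticist, who would probably notice a negative accumulation ratio. At the estimated half-life the true ratio is about 1 in any case.

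All of this stands, and it limits the consequence to the endpoint itself. It does not make the definition usable. SAP 8.1.1.2 is the written specification for the derivation, and a quiet correction in the software would be an undocumented departure from both documents.

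Could a minus sign have been lost when the PDF was read? That is unlikely. The positive exponent appears in four places and in more than one notation, and the other minus sign in the same expression survives each time.

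**Conclusion.** The definition is wrong as written. For every positive k and tau it returns a negative number equal to 1 minus the true predicted ratio: −0.0017 instead of 1.0017 at 1.3 h and 12 h, and −0.23 instead of 1.23 if the half-life were 5 h. The log-scale summary that the SAP prescribes for this endpoint cannot be computed from such values. The conclusion needs only a positive rate constant, which both documents use; the assumed half-lives affect the size of the error and not its sign. The error should be corrected before the endpoint is derived. It does not affect the observed accumulation ratios, the stopping criteria or any other planned analysis.

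**What to change.** Replace the formula with ARpred = 1/(1 − e^(−k·tau)) in SAP 2.2, SAP 8.1.1.2, the protocol synopsis and protocol section 4. State that k is lambda_z from the single-dose profile and is positive. Record the correction in SAP 2.1, which already notes one minor change to this objective.

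In the same edit, state which tau ARpred uses if three-times-daily dosing is chosen, because protocol Appendix 5 (7 h between doses) and SAP 2.2 (8 h AUC) must be reconciled on this point.

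The cost is one sign in two SAP places, and the same sign in two protocol places through whatever route the sponsor uses for protocol corrections. Data collection, sample size and the other analyses do not change.

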2.3. Study Design

Overview of Study Design and Key Features		
Figure 1 Study Design (Part A)		
Screening Period (28 days prior to D1)	Treatment Period	Follow-up Period (7-14 days post last dose)
Cohort 1 N = 8 (6A:2P)	DL1 → DL2 → DL3 → DL4 → 	
Cohort 2 N = 8 (6A:2P)	DL4 → DL5 → DL6 → DL7 → 	
Cohort 3 N = 14 (14A)	DLX →  DLX-FD → 	

All doses are fasted unless otherwise specified
 
♦ = Dose escalation meeting ◆ = Safety data review meeting
		
DL = Dose level; DLX = Dose level to be determined; FD = Fed Conditions; A = Active; P = Placebo		
Figure 2 Study Design (Part B)		
Screening Period (28 days prior to D1)	Treatment Period	Follow-up Period (7-14 days post last dose)
Cohort 4 N = 8 (6A:2P)	Repeat DL1 10 days → 	
Cohort 5 N = 8 (6A:2P)	Repeat DL2 10 days → 	
Cohort 6 N = 8 (6A:2P)	Repeat DL3 10 days → 	

♦ = Dose escalation meeting
 
DL = Dose level; A = Active; P = Placebo
 
Note: DL7 was not dosed in the study due to higher than expected exposures.
		
Design Features	
This study will be a randomized, double-blind (sponsor unblinded), placebo-controlled, 2-part study of the oral administration of GSK3186899A in healthy participants.
 
Planned to include approximately 54 participants and will consist of 2 parts as below:
 
 Part A will include a single-ascending, sequential crossover design in up to 3 cohorts of participants (Cohorts 1, 2 and 3). Part A Cohorts 1-2 will comprise of a 4 period crossover which includes 4 dosing regimens under fasted conditions. Part A Cohort 3 will comprise of a 2 period crossover which includes 1 dosing regimen 	

Overview of Study Design and Key Features	
	
under fasted conditions and 1 regimen under fed conditions. The fed conditions regimen will investigate the safety, tolerability and PK of a single dose of GSK3186899 following food administration.
 
 Part B will be a twice-daily (BID) 10-day repeat dose design in up to 3 parallel cohorts of participants (Cohorts 4, 5 and 6). Part B may include drug administration after either fed or fasted conditions, this will be dependent on the interim results from Part A. If under fasted conditions, participants will be required to fast at least 2 hours before and after drug administration.
Dosing	
 Part A (single ascending dose) For Part A, the dose escalation phase, up to 3 cohorts may be used (Cohorts 1-3). Cohorts 1 and 2 will consist of 8 healthy participants each. If used, Cohort 3 will consist of up to 14 healthy participants. 
 For Cohorts 1 and 2, each participant will receive a maximum of 3 ascending oral doses of GSK3186899 and 1 placebo dose under fasted conditions. At each dose level, GSK3186899 and placebo will be administered in a 3:1 ratio, within each period, according to the randomization schedule in a blinded manner. Up to a maximum of 7 dose levels will be studied in Part A as illustrated in Figure 1 above. For Cohort 3, each participant will receive 1 oral dose of GSK3186899 selected based on the results from Cohorts 1 and 2, under both fasted and fed conditions. For each cohort and within each treatment period (except Cohort 3), the first 2 participants will act as sentinels. No participant will be a sentinel participant more than once. On Day 1, 1 of the 2 sentinel participants will receive the active dose and the other will receive placebo. Based on the Principal Investigator's review of the 2 sentinel participants after at least the first 24hr post-dose safety data (e.g. vital signs, ECGs and AEs), the remaining 6 participants can then be randomized to dosing. Part B (repeat dose) For the repeat dose escalation phase in Part B, there will be up to 3 cohorts (Cohorts 4, 5 and 6), consisting of 8 healthy participants randomised to receive repeat doses of either GSK3186899 or placebo, administered in a 3:1 ratio according to the randomization schedule in a blinded manner. For BID dosing, GSK3186899 or placebo will be administered using a 12hr dosing interval. Based on emerging data in Part A, an alternate dosing regimen (OD or TID) may be selected if deemed suitable. 
 The first 2 participants in each cohort in Part B will act as sentinels. On Day 1 until Day 10, 1 of the 2 sentinel participants will receive the active dose twice daily and the other will receive placebo twice daily. Once these participants have completed their first 5-days of dosing, the safety and tolerability data will be reviewed by the Principal Investigator. If there are no clinically relevant safety or tolerability concerns (e.g. vital signs, ECGs and AEs) the remaining 6 participants will be randomized to dosing.
Time & Events	
 Refer to Appendix 2: Schedule of Activities
Treatment Assignment	
 Part A consists of up to 30 participants in up to 3 cohorts (excluding possible replacements): 
 Cohort 1 and 2 will each have 6 participants in active versus 2 participants in placebo (i.e., in a 3:1 ratio)

Overview of Study Design and Key Features	
	
 ○ Cohort 3 will contain up to 14 participants in a 1:1 ratio for (fed and active) versus (fasted and active) ● Part B consists of up to 24 participants in up to 3 cohorts: 
 ○ Cohorts 4, 5 and 6 will each have 6 participants in active versus 2 participants in placebo (i.e., in a 3:1 ratio)
Interim Analysis	
No formal interim analyses (IA) are planned for this study. However, safety, tolerability, and PK data will be reviewed before each dose escalation in Part A (single dose) and Part B (repeat dose), prior to the investigation of the food effect, and between Part A and Part B.
 
An informal interim analysis for Part A will be conducted prior to initiating Part B. This analysis will support the decision to progress or not to progress to Part B.

